3.1.1 Administrative structure of the trial

The trial is sponsored by Boehringer Ingelheim (BI) Pharma GmbH & Co. KG, Germany.

BI has appointed a Trial Clinical Monitor, responsible for coordinating all required activities, in order to

- manage the trial in accordance with applicable regulations and internal SOPs,

Proprietary confidential information © 2018 Boehringer Ingelheim International GmbH or one or more of its affiliated companies

- direct the clinical trial team in the preparation, conduct, and reporting of the trial,
- ensure appropriate training and information of local clinical monitors (CML), Clinical Research Associates (CRAs), and participating trial sites.

The trial medication will be provided by the Clinical Trial Supplies Unit (CTSU), BI Pharma GmbH & Co. KG, Biberach, Germany.

The trial will be conducted at the

, under the supervision of the Principal Investigator.

Safety laboratory tests will be performed by the local laboratory of the trial site

The digitally recorded 12-lead ECGs will be sent to a specialised contract research organisation () for evaluation.

On-site monitoring will be performed by BI or a contract research organisation appointed by BI.

Data management and statistical evaluation will be done by BI or a contract research organisation appointed by BI and according to BI SOPs.

Tasks and functions assigned in order to organise, manage, and evaluate the trial are defined according to BI SOPs. A list of responsible persons and relevant local information can be found in the ISF.

3.2 DISCUSSION OF TRIAL DESIGN, INCLUDING THE CHOICE OF CONTROL GROUP

For single-rising dose trials, the design described in [Section 3.1](#) is viewed favourable under the provision not to expose the subjects involved to undue risks since the main study objective is to investigate safety and tolerability of BI 1323495.

With the rising dose design, single-blind conditions regarding the subject's treatment (active or placebo) are maintained within each dose group. However, the current dose level will be known to subjects and investigators. The disadvantage of this trial design is a possible observer bias with regard to the dose-depending effects as well as time effects, but it has the virtue of minimizing subject risk by sequentially studying ascending doses. As time-effects are expected to be small relative to the differences between the doses in the broad range investigated, unbiased comparisons between treatments can still be expected.

Proprietary confidential information © 2018 Boehringer Ingelheim International GmbH or one or more of its affiliated companies

It is standard in trials involving healthy volunteers to include a placebo group as control for the evaluation of safety and tolerability. Each dose group consists of 8 subjects with 6 on active treatment, and 2 on placebo. The placebo control group includes all subjects of all dose groups treated with placebo. 6 subjects per active treatment group are in general considered as sufficient for the exploratory evaluation of pharmacokinetics.

3.3 SELECTION OF TRIAL POPULATION

It is planned that 64 healthy male subjects will enter the study. The actual number of subjects entered may exceed the total of 64 if additional intermediate doses will be tested (see [Section 3.1](#)). Subjects will be recruited from the volunteers' pool of the trial site.

Only male subjects will be included into the study because hitherto no data on reproductive toxicology are available.

A log of all subjects enrolled into the trial (i.e. having given informed consent) will be maintained in the ISF at the investigational site irrespective of whether they have been treated with investigational drug or not.

3.3.1 Main diagnosis for study entry

The study will be performed in healthy subjects.

3.3.2 Inclusion criteria

Subjects will only be included into the trial, if they meet the following criteria:

1. Healthy male subjects according to the assessment of the investigator, based on a complete medical history including a physical examination, vital signs (BP, PR), 12-lead ECG, and clinical laboratory tests
2. Age of 18 to 45 years (incl.)
3. BMI of 18.5 to 29.9 kg/m² (incl.)
4. Signed and dated written informed consent prior to admission to the study in accordance with GCP and local legislation

3.3.3 Exclusion criteria

Subjects will not be allowed to participate if any of the following general criteria apply:

1. Any finding in the medical examination (including BP, PR or ECG) is deviating from normal and judged as clinically relevant by the investigator
2. Repeated measurement of systolic blood pressure outside the range of 90 to 140 mmHg, diastolic blood pressure outside the range of 50 to 90 mmHg, or pulse rate outside the range of 50 to 90 bpm
3. Any laboratory value outside the reference range that the investigator considers to be of clinical relevance
4. Any evidence of a concomitant disease judged as clinically relevant by the investigator

Proprietary confidential information © 2018 Boehringer Ingelheim International GmbH or one or more of its affiliated companies

5. Gastrointestinal, hepatic, renal, respiratory, cardiovascular, metabolic, immunological or hormonal disorders
6. Cholecystectomy and/or surgery of the gastrointestinal tract that could interfere with the pharmacokinetics of the trial medication (except appendectomy and simple hernia repair)
7. Diseases of the central nervous system (including but not limited to any kind of seizures or stroke), and other relevant neurological or psychiatric disorders
8. History of relevant orthostatic hypotension, fainting spells, or blackouts
9. Chronic or relevant acute infections
10. History of relevant allergy or hypersensitivity (including allergy to the trial medication or its excipients)
11. Use of drugs within 30 days prior to administration of trial medication if that might reasonably influence the results of the trial (incl. QT/QTc interval prolongation)
12. Participation in another trial where an investigational drug has been administered within 60 days prior to planned administration of trial medication, or current participation in another trial involving administration of investigational drug
13. Smoker (more than 10 cigarettes or 3 cigars or 3 pipes per day)
14. Inability to refrain from smoking on specified trial days
15. Alcohol abuse (consumption of more than 30 g per day)
16. Drug abuse or positive drug screening
17. Blood donation of more than 100 mL within 30 days prior to administration of trial medication or intended donation during the trial
18. Intention to perform excessive physical activities within one week prior to administration of trial medication or during the trial
19. Inability to comply with dietary regimen of trial site
20. A marked baseline prolongation of QT/QTc interval such as QTc intervals that are repeatedly greater than 450 ms or any other relevant ECG finding at screening
21. A history of additional risk factors for Torsades de Pointes (such as heart failure, hypokalemia, or family history of Long QT Syndrome)
22. Subject is assessed as unsuitable for inclusion by the investigator, for instance, because considered not able to understand and comply with study requirements, or has a condition that would not allow safe participation in the study

23. Male subjects with female partner of childbearing potential who are unwilling to use male contraception (condom or sexual abstinence) from the first administration of trial medication until 30 days after last administration of trial medication
24. Current or history of relevant kidney, urinary tract diseases or abnormalities (e.g. nephrolithiasis, hydronephrosis, acute or chronic nephritis, renal injury, renal failure)
25. Estimated glomerular filtration rate according to CKD-EPI formula < 90 mL/min at screening ([R12-1392](#))
26. Within 10 days prior to administration of trial medication, use of any drug that could reasonably inhibit platelet aggregation or coagulation (e.g., acetylsalicylic acid)

Proprietary confidential information © 2018 Boehringer Ingelheim International GmbH or one or more of its affiliated companies

27. Liver enzyme (ALT, AST, GGT) values above upper limit of normal at the screening examination

For study restrictions, refer to [Section 4.2.2](#).

3.3.4 Removal of subjects from therapy or assessments

3.3.4.1 Removal of individual subjects

An individual subject is to be removed from the trial if:

1. The subject withdraws consent for trial treatment or trial participation, without the need to justify the decision
2. The subject needs to take concomitant drugs that interfere with the investigational product or other trial medication
3. The subject is no longer able to participate for other medical reasons (such as surgery, adverse events (AEs), or diseases)
4. The subject shows an elevation of AST and/or ALT \geq 3-fold ULN combined with an elevation of total bilirubin \geq 2-fold ULN (measured in the same blood sample) and/or needs to be followed up according to the 'DILI checklist' provided in the ISF.

A subject can also be removed from the trial if eligibility criteria are being violated or if the subject fails to comply with the protocol (for instance, by non-adherence to dietary rules, or non-attendance at study assessments).

If a subject is removed from or withdraws from the trial prior to first administration of trial medication, the data of this subject will not be entered in the case report form (CRF) or trial database and will not be reported in the clinical trial report (CTR). If a subject is removed from or withdraws from the trial after first administration of trial medication, this will be documented and the reason for discontinuation must be recorded in the CRF. In this case, the data will be included in the CRF/trial database and will be reported in the CTR. At the time of discontinuation a complete end of trial examination will be performed if possible and the information will be recorded in the CRFs. If the discontinuation occurs before the end of the REP (see [Section 5.2.2.2](#)), the discontinued subject should if possible be questioned for AEs and concomitant therapies at or after the end of the REP in order to ascertain collection of AEs and concomitant therapies throughout the REP, if not contrary to any consent withdrawal of the subject. These discontinuations will be discussed in the CTR.

3.3.4.2 Discontinuation of the trial by the sponsor

Boehringer Ingelheim reserves the right to discontinue the trial overall or at a particular trial site at any time for any of the following reasons:

1. New toxicological findings or serious adverse events invalidate the earlier positive benefit-risk-assessment. Dose escalation will be terminated if more than 50% of the subjects at one dose level show drug-related and clinically relevant adverse events of moderate or severe intensity.

Proprietary confidential information © 2018 Boehringer Ingelheim International GmbH or one or more of its affiliated companies

No further subjects will be dosed without thorough re-evaluation of the benefit-risk ratio, if severe non-serious adverse events considered as drug-related by the investigator are reported in 2 subjects of the same dose group or if at least one drug-related serious adverse event is reported.

2. The expected enrolment goals overall are not met
3. Violation of GCP, or the CTP by a trial site or investigator, disturbing the appropriate conduct of the trial
4. The sponsor decides to discontinue the further development of the investigational product.
5. Dose escalation will be stopped as soon as at least 2 subjects at one dose level on active drug showed relevant individual QT prolongation, i.e. absolute QT or QTc greater than 500 which has been confirmed by a repeat ECG recording or QTc increase of greater 60 ms from baseline in connection with absolute QT or QTc greater than 500 ms, which has been confirmed by a repeat ECG recording.
6. Dose escalation will be stopped if the C_{max} or AUC_{0-24} of at least 1 subject of one dose group increases above the following exposure thresholds or if the estimated systemic exposure (group gMean values) of the next dose level is expected to exceed a C_{max} of nM or an AUC_{0-24} of nM*h. In this case, one or two dose levels lower than the planned next dose level may be given, as long as the expected systemic exposure (group gMean values) of each dose is not expected to exceed the aforementioned thresholds.

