- A thorough ECG monitoring including continuous ECG measurement over 4 hours post-dose and repeated 12-lead ECGs during the observation period following drug administration. Dose escalation would be stopped as soon as at least 2 subjects at one dose level showed relevant QT prolongation (see [Section 3.3.4.2](#) for details).
- The subjects will stay at the trial site (BI Human Pharmacology Centre) for at least 34 hours after study drug administration. Based on an anticipated half-life of BI 1323495 of approximately _____ this is expected to cover the period of highest risk / peak effect.
- During in-house confinement the subjects will be under medical observation and thoroughly monitored for both expected and unexpected adverse events.

In summary, although not tested in humans to date, BI 1323495 has the potential to become an oral treatment for patients with _____. Based upon preclinical data for BI 1323495 and clinical information from competitor compounds as well as the implemented safety measures described above, healthy subjects will not be exposed to undue risks in relation to the important information expected from this trial as a basis for further clinical development of this compound. Healthy volunteers are not expected to have any direct benefit from participation in this first-in-man clinical trial with BI 1323495. Considering the medical need of the development of an effective treatment for patients with _____ the Sponsor considers

Proprietary confidential information © 2018 Boehringer Ingelheim International GmbH or one or more of its affiliated companies

that the benefit outweighs the potential risks and justifies exposure of healthy human volunteers.

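### In the QT stopping rule, the limb based on a QTc rise of more than 60 ms lies wholly inside the 500 ms limb, so it can never stop escalation on its own

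*Protocol*

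**What the plan says.** Protocol 3.3.4.2, criterion 5, opens with the count: "Dose escalation will be stopped as soon as at least 2 subjects at one dose level on active drug showed relevant individual QT prolongation". It then defines such prolongation by two alternatives.

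- Limb 1: "absolute QT or QTc greater than 500 which has been confirmed by a repeat ECG recording". No unit is printed after the 500.
- Limb 2: "QTc increase of greater 60 ms from baseline in connection with absolute QT or QTc greater than 500 ms". It carries the same confirmation requirement: "greater than 500 ms, which has been confirmed by a repeat ECG recording".

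The connector is a plain alternative: "confirmed by a repeat ECG recording or QTc increase of greater 60 ms from baseline".

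Protocol 2.3.3 lists the rule among the trial's safety measures: "Dose escalation would be stopped as soon as at least 2 subjects at one dose level showed relevant QT prolongation". It points to 3.3.4.2 for the detail and gives no definition of its own.

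Protocol 3.1 makes dosing and escalation conditional on none of the 3.3.4.2 criteria having been met. At entry, exclusion criterion 20 keeps out men with a marked prolongation, such as "QTc intervals that are repeatedly greater than 450 ms".

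**The concern.** A rule with two alternatives, each with its own number, reads as two ways of being triggered: a high absolute value and a large change from baseline. Here the change limb also requires the absolute value that already suffices for the other limb. The 60 ms figure then does no work.

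This is the only numerical QT stopping rule in the visible text of a first-in-human protocol. A team applying it literally would count no qualifying subject among men with large confirmed QTc rises whose QT and QTc both stay at or below 500 ms, although the rule itself names a rise of more than 60 ms. The documents do not show whether the sponsor wanted an absolute limit only or a rise limb with its own effect.

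**Working it through.** The plan offers no figure to reproduce here, so the check is one of logic followed by simple arithmetic.

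**Logic.** Let A = QT or QTc above 500 ms, confirmed on a repeat ECG. Let B = QTc rise above 60 ms and QT or QTc above 500 ms, both confirmed. B is A plus one condition, so B is a subset of A, and (A or B) = A.

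**Enumeration.** The two limbs were also evaluated over an assumed grid for the first and repeat ECG: baseline QTc 340 to 450 ms and post-dose QTc 340 to 600 ms in steps of 10, and post-dose QT 340 to 600 ms in steps of 20. That gives 12 × 27² × 14² = 1,714,608 combinations.

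- A met: 607,500
- B met: 318,101
- B met without A: 0
- Largest confirmed QTc rise with neither QT nor QTc above 500 ms: 160 ms (340 to 500 ms)

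The counts depend on the grid. The zero does not, because it follows from the logic.

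**Rise needed, on QTc alone.** The rise needed is more than 500 − baseline. These figures assume that uncorrected QT also stays at or below 500 ms.

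| Baseline QTc (ms) | QTc at which the rise passes 60 ms | Rise needed for QTc to pass 500 ms |
|---|---|---|
| 380 | > 440 | > 120 |
| 400 | > 460 | > 100 |
| 420 | > 480 | > 80 |
| 440 | > 500 | > 60 |
| 450 | > 510 | > 50 |

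At 440 ms the two thresholds coincide, but it is limb 1 that acts. Above 440 ms limb 1 acts at a rise of less than 60 ms.

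**Effect of uncorrected QT.** Limb 1 also fires on QT itself, so heart rate matters. Exclusion criterion 2 admits pulse rates down to 50 bpm, and the abbreviations list gives Fridericia or Bazett as the correction. With Fridericia, QTcF = QT / RR^(1/3), where RR = 60 / heart rate in seconds.

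- At 50 bpm, RR = 1.2 s and RR^(1/3) = 1.0627. QT of 500 ms is QTcF = 500 / 1.0627 = 470.5 ms. The rise needed falls to about 70 ms from a baseline of 400 ms and about 50 ms from 420 ms.
- Suppose all 6 active subjects in a dose group go from QTcF 400 to 490 ms, a rise of 90 ms. QT stays at or below 500 ms only if RR ≤ (500 / 490)³ = 1.0625 s, which is 60 / 1.0625 = 56.5 bpm. At about 57 bpm or faster there are 0 qualifying subjects. At 50 bpm, QT = 490 × 1.0627 = 521 ms, and each subject qualifies if the value is confirmed.

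**The case against.** The strongest reply is that redundant wording does no harm. The operative rule is clear: two active subjects at one dose level with a confirmed QT or QTc above 500 ms. Deleting limb 2 would change no decision. The sentence ties the rise to the 500 ms value in so many words, and 2.3.3 mentions no rise criterion. This stands as far as it goes. The rule can be applied, and the documents do not promise a separate rise safeguard. It does not explain why a threshold with no effect appears in a stopping rule, or what that threshold was meant to do.

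A second reply is that judgement covers the gap. Protocol 3.1 requires that the Principal Investigator and the trial clinical monitor have no safety concern before escalation, and lets the investigator or sponsor stop it. Section 5.2.4.1 requires ECG abnormalities to be monitored carefully and reported as adverse events if clinically relevant. So a reader who infers that men with large rises below 500 ms would be unprotected goes too far. These controls are discretionary, however, and do not make limb 2 operative. In the visible text, the minimum data set for the safety review in 3.1 has no separate ECG item, and its check of stopping criteria cites 3.3.4.1, which contains no QT criterion.

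A third reply is that the repeat ECG might need to confirm only the rise. Limb 2 could then be met alone, for example with baseline 430 ms, first QTc 505 ms (rise 75), repeat QTc 495 ms (rise 65) and QT not above 500 ms on the repeat. The wording does not suggest this reading. Even then one value above 500 ms is needed, so a rise by itself still stops nothing.

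**Conclusion.** The point holds. Limb 2 of criterion 5 adds no stopping case to limb 1, the 60 ms figure affects no stopping decision, and the rule is an absolute limit only. This rests on the natural reading that the repeat ECG confirms the whole of limb 2.

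The size of the gap depends on baseline and heart rate. On QTc alone, with uncorrected QT at or below 500 ms, rises of up to 120, 100 or 80 ms from baselines of 380, 400 or 420 ms meet neither limb. At slow heart rates the gap narrows or closes, because QT itself reaches 500 ms first.

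Three stronger readings are not supported:

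- That limb 2 can never be met. It can be, but only when limb 1 is met too.
- That a dose group rising from 400 to 490 ms would never trigger the rule. That needs heart rates of about 57 bpm or faster, with Fridericia correction.
- That 450 ms caps the baseline. Exclusion criterion 20 is a screening rule about repeated values, given as an example, whereas SAP 6.7 takes baseline as the last measurement before dosing.

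The documents also do not show that the sponsor intended an independent rise criterion. They show only that the text has two limbs and one effect.

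**What to change.** The sponsor should reconcile the two limbs of criterion 5 in 3.3.4.2 and state what the 60 ms rise is meant to add. Two outcomes would be coherent:

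- the rise limb is worded so that it has an effect of its own; or
- the rise limb is removed, and 3.3.4.2 and 2.3.3 both state that only the absolute limit stops escalation.

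Which of these is right, and at what value, is a clinical decision for the sponsor. No threshold is proposed here. The unit missing after the first 500 should be added at the same time.

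The cost is about one sentence in a protocol amendment, with a matching line in 2.3.3 if the limb is removed. No new measurements are needed, since the present rule already calls for a baseline and a confirmed post-dose value. Removing the limb changes no decision. Giving it effect would add some chance of a pause in escalation, which cannot be sized because the visible text gives no QTc variability.

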Proprietary confidential information © 2018 Boehringer Ingelheim International GmbH or one or more of its affiliated companies

concerns exist in the opinion of the Principal Investigator (or an authorised deputy) and the trial clinical monitor (or an authorised deputy).

Although no formal Safety Review meeting will take place within a given dose group, safety will be continuously monitored during this trial, and an individual will only be dosed in the absence of any safety concern (i.e., no dose-limiting events occurred) and if none of the pre-specified trial-specific stopping criteria have been met (refer to [Section 3.3.4.2](#)).

The minimum data set for review consists of the following data:

- AEs in the current* and preceding dose groups including clinically relevant findings from ancillary safety testing listed below up to at least 48 h post-dosing.
Note: AEs may be ongoing at the time of Safety Reviews and AE information may be subject to change prior to Database Lock.
- Vital signs in the current* and preceding dose groups up to at least 48 h post-dosing
- Clinical laboratory tests in the current* and preceding dose groups up to at least 24 hours post-dose
- Preliminary PK data for selected time points as per [Section 7.3.4](#)
- Check of criteria for stopping subject treatment as per [Section 3.3.4.1](#)

**"Current dose group" means: all subjects of that dose group with at least 4 subjects being on active treatment.

The decision to escalate the dose will be made jointly by the Principal Investigator (or an authorised deputy) and the trial clinical monitor (or an authorised deputy) after in-depth analysis of all available safety data, especially SAEs (if occurred), AEs, and out-of-range laboratory results (if considered clinically significant). Safety Reviews can be conducted face-to-face or by video/telephone conference. The trial clinical monitor is responsible for organization and minutes of the reviews. Minutes will be signed off by the Principal Investigator (or an authorised deputy) and filed in the ISF and TMF.

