7.3.4 Preliminary PK analyses

A preliminary analysis of PK parameters (AUC_{0-24} and C_{max} of BI 1323495) provided as individual values and geometric means will be performed for

- DG 1 before proceeding to DG 3
- DG 1-2 before proceeding to DG 4
- DG 1-4 before proceeding to DG 5
- DG 1-5 before proceeding to DG 6
- DG 1-6 before proceeding to DG 7
- DG 1-7 before proceeding to DG 8

Note: Data from the first cohorts of the above mentioned dose levels will be sufficient as long as the data from at least 2 subjects on active were available.

Proprietary confidential information © 2018 Boehringer Ingelheim International GmbH or one or more of its affiliated companies

In contrast to the final PK/PD calculations, the preliminary analysis will be based on planned sampling times rather than on actual times, regardless of whether actual times were within the time windows or not. Therefore, minor deviations of preliminary and final results may occur. The preliminary analysis will provide individual and mean concentration/effect-time profiles and summary statistics of individual values without subject identification. The preliminary results will be distributed to the Investigator and the trial team.

Depending on the results of available preliminary PK/PD analyses, the tolerability and safety of the compound, and changes of dosing schedule (e.g. additional intermediate doses) additional PK/PD preliminary analysis may be performed based on the request of the Trial Clinical Monitor, the investigator, or Trial Clinical Pharmacokineticist. No formal preliminary PK report will be written.

No inferential statistical interim analysis is planned. However, after each dose group the investigator (or deputy) is allowed to postpone further dose progression until a preliminary analysis of the data already obtained has been performed.

The pharmacokinetic parameters AUC_{0-24} and C_{max} for BI 1323495 will be calculated according to the BI SOP

will be performed using the validated software program
quality check of the interim data will be performed.

The non-compartmental analysis
A

Available
information on dose linearity from preceding dose groups will be considered when estimating C_{max} and AUC values to be expected for the next higher dose to be administered.

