7.5 RANDOMISATION

Each dose group will be divided into three cohorts. The subjects of the first and second cohorts will not be randomised to maintain a treatment sequence of active-placebo-active-active due to safety reasons. In the third cohort of each dose level the subjects will be assigned to active or placebo treatment using a 3:1 allocation ratio.

The sponsor will arrange for the randomisation as well as packaging and labelling of trial medication. The randomisation list will be generated using a validated system, which involves a pseudo-random number generator and a supplied seed number so that the resulting allocation is both reproducible and non-predictable.

Proprietary confidential information © 2018 Boehringer Ingelheim International GmbH or one or more of its affiliated companies

The randomisation list will contain additional blocks to allow for subject replacement (refer to [Section 3.3.5](#)).

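### Any one subject over the exposure limit stops escalation, but the PK check before the next dose may rest on 2 or 3 of the 6 active subjects

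*Protocol*

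**What the plan says.** Protocol Section 3.3.4.2, criterion 6, has two exposure triggers. Escalation stops if the Cmax or AUC0-24 "of at least 1 subject of one dose group increases above the following exposure thresholds", or if the geometric mean (gMean) predicted for the next dose is too high. The limits are blacked out. Section 2.1.2 likewise makes the maximum dose depend on individual values at lower doses, judged from the interim PK of Section 7.3.4.

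Section 7.3.4 lists which groups' PK must be analysed before each step. From "DG 1-4 before proceeding to DG 5" onward, the immediately preceding group is included. A note then says that data from the first cohorts "will be sufficient as long as the data from at least 2 subjects on active were available".

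Section 7.5 leaves the first two cohorts unrandomised to "maintain a treatment sequence of active-placebo-active-active due to safety reasons". They therefore hold 3 active subjects; cohort 3 holds the other 3.

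Section 3.1 sets the minimum data for each Safety Review. The AE, vital-sign and laboratory items refer to the current dose group, defined as "all subjects of that dose group with at least 4 subjects being on active treatment". The PK item carries no such marker. It reads "Preliminary PK data for selected time points as per" Section 7.3.4.

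Two general safeguards apply. Under Section 3.1 an individual is dosed only "if none of the pre-specified trial-specific stopping criteria have been met" (and there is no safety concern). Under Section 7.3.4, after each group "the investigator (or deputy) is allowed to postpone further dose progression until a preliminary analysis of the data already obtained has been performed".

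**The concern.** Two or three subjects may serve to project a geometric mean. They cannot verify a rule that any one of six can trigger. A breach in a subject whose samples are not yet analysed is unknown to the people deciding on escalation, and the bar on dosing after a stopping criterion is met cannot act on an unread sample. No visible text requires cohort 3 PK to be read before the next group starts.

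This is a first-in-human trial, and the individual exposure limit is one of its stated safeguards. Following the plan exactly, subjects could receive a higher dose after someone at the lower dose had already exceeded the limit. The protocol itself uses a higher minimum, 4 on active, for the other review data, so the lower PK minimum stands out.

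**Working it through.** **Group structure.** Active subjects by cohort: 1 + 2 + 3 = 6. Placebo: 1 + 0 + 1 = 2. Eight groups of 8 give 64, as planned. There is no power calculation to reproduce (Section 7.6).

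**Chance of missing a breach that exists.** With k of 6 active subjects over the limit and m read, the miss probability is C(6-k, m)/C(6, m). This treats the subjects read as exchangeable with those not read.

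| Over the limit | 2 read | 3 read | 4 read | 6 read |
|---|---|---|---|---|
| k = 1 | 10/15 = 67% | 10/20 = 50% | 5/15 = 33% | 0% |
| k = 2 | 6/15 = 40% | 4/20 = 20% | 1/15 = 7% | 0% |

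**Chance that a breach occurs and is missed.** Let p be the per-subject breach probability and q = 1 - p. With independent subjects the probability is q^m - q^6. The documents give neither the limits nor the variability, so p is an assumption and a range is shown.

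| p | 2 read | 3 read | 4 read |
|---|---|---|---|
| 5% | 16.7% | 12.2% | 7.9% |
| 10% | 27.9% | 19.8% | 12.5% |
| 20% | 37.8% | 25.0% | 14.7% |
| 30% | 37.2% | 22.5% | 12.2% |
| Maximum over p | 38% (p = 0.240) | 25% (p = 0.206) | 15% (p = 0.184) |

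The last row is an upper bound. It ignores criterion 6's second trigger, the predicted gMean.

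**Consequence in subjects dosed.** The inputs are the minimum intervals in Section 2.3.3, counted from the first dose of the preceding group:

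- Cohort 3 is dosed at 48 h, and its 0-24 h sampling ends at 48 + 24 = 72 h.
- The 48 h AE and vital-sign data on at least 4 active subjects are complete at 48 + 48 = 96 h. The fourth active subject is in cohort 3, so the Safety Review already waits for that cohort.
- The next group's cohort 1 (1 active) starts at 6 days = 144 h, cohort 2 (2 more) at 168 h, and cohort 3 (3 more) at 192 h.

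The cut-offs for cohort 3 PK turnaround, counted from 72 h, are 144 - 72 = 72 h, 168 - 72 = 96 h and 192 - 72 = 120 h.

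| Turnaround | Next-group active subjects dosed first |
|---|---|
| up to 72 h | 0 |
| over 72 to 96 h | 1 |
| over 96 to 120 h | 3 |
| over 120 h | up to 6 |

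**Size of the dose steps.** Tablet counts within one unit strength (Section 4.1.1) give DG 4 to DG 5 as 4/2 = 2.0, DG 5 to DG 6 as 6/4 = 1.5, and DG 7 to DG 8 as 4/3 = 1.33.

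**The case against.** The strongest reply is that this is an openly stated operating choice. Two is a floor, not a cap. PK lags safety data by design: no analysis is listed before DG 2, only DG 1 before DG 3, and only DG 1-2 before DG 4. Nothing says the PK minimum must match the safety minimum, and the usual figure of 3 is inferred from cohort make-up. This stands as context. From DG 5, however, the plan does require the preceding group's PK, and what that check is worth against an any-one-subject rule depends on how many are read.

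Second, a reader might take 38% or 25% as the risk that escalation wrongly goes ahead. The documents do not support that. At the breach rates behind those maxima, the predicted-gMean trigger would often stop escalation anyway. Assume log-normal exposure, dose proportionality and one common limit. At p = 0.240 and 0.206 the true gMean lies 0.71 and 0.82 log-SD below the limit. A 1.5-fold step would then be expected to take the predicted gMean over the limit unless the between-subject CV exceeds about 62% or 53%. For a 1.33-fold step the figures are about 42% and 36%; for a doubling, over 100%. This objection stands, although a gMean estimated from few subjects is noisy.

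Third, a reader might infer that the stop is lost or that dosing is unsafe. Neither follows. Criterion 6 has no time limit, the listed analyses are cumulative, and a known breach bars further dosing. The exposure cap also sits 10- to 34-fold below the toxicology reference exposures (Section 2.1.2). Taking the lowest factor and assuming proportionality, exposure just over the cap followed by a 1.5- or 2-fold step leaves about 10/1.5 = 6.7-fold or 10/2 = 5-fold.

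Fourth, criterion 6 goes on to allow one or two reduced dose levels, subject to the expected gMean, without saying which trigger this follows. It could be read to allow, after an individual breach, a dose above the breaching dose on a gMean check alone. Other text points against that. Section 2.1.2 stops escalation at lower doses, Section 3.1 gives the next dose only if no stopping criterion was met, and Section 7.6 allows additional doses only if none applies. Section 2.3.3 requires a safety interim analysis and a substantial amendment for further progression, though it may mean only progression beyond the threshold. Blacked-out text in criterion 6 may settle the matter, so this is a wording question and not a contradiction.

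**Conclusion.** The mismatch is real and worth fixing. A stop that any one of six subjects can trigger may be checked on 2 or 3 of them, fewer than the 4 required for the other safety data. If exactly one subject is over the limit, the check misses him with probability 67% or 50%, against 33% at the 4-active minimum and 0% with all six. These figures need only exchangeability, not the blacked-out limits. They are conditional on a breach and say nothing about how likely one is.

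The consequence is a delayed stop. It costs nothing if cohort 3 turnaround is 72 h or less, and at most 6 active subjects of the next group if it exceeds 120 h. That range rests on the minimum intervals and on a turnaround the documents do not state. No endpoint, sample size or final analysis is affected. The question of which doses are open after a breach is a secondary clarification.

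**What to change.** In Section 7.3.4, from DG 5 onward, require preliminary PK from at least the same 4 active subjects of the immediately preceding group that the Safety Review already needs, and from all 6 where turnaround permits. Mark the PK item in Section 3.1 with the same current-dose-group definition. Starting at DG 5 adds no new analysis: the preceding group is already listed there, and DG 4 to DG 5 doubles the dose. Four subjects narrow the gap (a single breach is still missed with probability 33%); only six close it.

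The cost is amendment wording and possible delay. The samples are already drawn. On the minimum intervals about 72 h remain for assay, non-compartmental analysis and quality check before the next group can start. Escalation slips if turnaround is longer, and a later cohort 3 dosing shortens the window hour for hour.

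As a clarification, state in Section 3.3.4.2(6) that the reduced-dose option applies to the predicted-gMean trigger. State also that, after an individual breach, no dose above the breaching dose is given without the safety interim analysis and substantial amendment of Section 2.3.3. This could delay intermediate doses after a breach.
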